## **Statistical Methods:**

1. For the primary objective:

The test for non-inferiority will be carried out using a two-tailed 95% confidence interval for the difference in the rate of catheterization between the two voiding methods, within the six-week post-operative period,  $\delta$  ( $\delta$ =rate of catheterization in the FAST voiding trial – rate of catheterization in the Traditional voiding trial). This difference,  $\delta$ , is the margin of non-inferiority and will be set at 10%. If the upper confidence limit for the difference is  $<\delta$  ( $\ge\delta$ ) then we will conclude that the FAST voiding trial is non-inferior (inferior) to the Traditional voiding trial.

The test for non-inferiority will be performed only for the primary outcome variable of interest, i.e., catheterization within the six-week post-operative period among subjects who were discharged without needing a urinary catheter.

The test for non-inferiority will also be performed according to surgery type (the stratification variable).

- For the secondary objectives:
  - a. The chi-square test or Fisher's exact test, as appropriate, will be used to compare the two voiding methods with respect to the proportion of subjects who are sent home with a catheter due to failure of their voiding trial, post-surgery.
  - b. The chi-square test or Fisher's exact test, as appropriate, will be used to compare the two voiding methods with respect to the proportion of subjects who present with any UTI within the six-week post-operative period. If feasible, the incidence of UTIs will be compared between the two voiding methods using the Incidence Density Ratio Method, or if feasible, Poisson regression methods.
  - c. The chi-square test or Fisher's exact test, as appropriate, will be used to compare the two voiding methods with respect to the proportion of subjects who present to the emergency room or the urogynecology clinic (unexpectedly) due to voiding dysfunction or suspected infection, within the six-week post-operative period. If feasible, the incidence of ER visits or unexpected clinic visits will be compared between the two voiding methods using the Incidence Density Ratio Method, or if feasible, Poisson regression methods.

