#### Sample Size Considerations:

The proposed sample size for this one year study is a total of 154 evaluable subjects (n=77 randomized to each voiding group). A subject will be "evaluable" if she gets randomized and is able to undergo the voiding trial. A subject who is not able to undergo the voiding trial is considered "not evaluable" and would not be included in the analysis.

The study will be designed as a non-inferiority trial, where the FAST voiding trial will be considered non-inferior to the Traditional voiding trial if the difference in the rate of catheterization between the two groups within the six-week post-operative period among patients discharged without a catheter is less than  $\delta$ =10% (i.e.  $\delta$ =10%, the margin of non-inferiority). More formally, if the rates of catheterization during the six-week post-operative period are p\_F and p\_T, respectively for the FAST and Traditional voiding methods, then the null (Ho) and alternative hypotheses (HA) are:

$$H_0$$
:  $d = p_F - p_T \ge \delta$  vs.  
 $H_A$ :  $d = p_F - p_T < \delta$ 

Based on the investigators' clinical experience, it can be reasonably assumed that among those who pass the Traditional retrograde fill voiding trial, the rate of catheterization during the six-week post-operative period is about 5%. Further assuming that the rate of catheterization among those who pass the FAST voiding trial is the same as in the traditional voiding test (i.e. 5% as well), and using a non-inferiority margin, $\delta$ , of 10%, then a sample size of 59 per group (n=118 total) will yield 80% power to determine that the FAST voiding trial is not inferior to the Traditional voiding trial (alpha=0.05).

Based on published manuscripts, about 30% of evaluable patients will fail either voiding trial, that is, approximately 30% in the traditional retrograde fill voiding trial arm will fail the test and similarly, approximately 30% in the FAST voiding trial arm will fail the test. Therefore, in order to obtain 118 subjects who pass the voiding test (59 per group), we would need to have a total of 154 subjects (118 x 1.3=154).

Randomized subjects will fall into three groups:

- 1. Subjects with a complication at surgery that would require prolonged catheterization immediately postoperative.
- 2. Subjects who fail either voiding test and are discharged home with a catheter (expected to be 25-26% based on pusblished manuscripts)

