- Subjects passing either trial of void and discharged home without a
  catheter. This is the main population of interest that we want to
  examine to identify what proportion of subjects would end up
  needing a catheter ultimately in the 6-week postoperative period.

Below is a tabulation of sample size requirements for 80% power, using various assumptions for the rates of catheterization during the six-week post-operative period in each of the two

Version Date: 2/26/16 Page 12 of 25

voiding methods, using a 2-sided alpha level of 0.05, and a non-inferiority margin,  $\delta$ , of 10%:

Traditional	FAST Voiding	Sample Size
Voiding Method	Method	Per Method (N)
0.05	0.07	109
0.05	0.06	80
0.05	0.05	59
0.05	0.04	44
0.05	0.03	33

Version Date: 2/26/16 Page 13 of 25

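### The primary decision rule calls FAST inferior whenever the upper 95% limit reaches 10 points, although that result shows only that non-inferiority was not demonstrated

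*Combined protocol and SAP*

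**What the plan says.** The combined protocol and SAP, section 12, Statistical Methods, states that the primary test is "carried out using a two-tailed 95% confidence interval for the difference in the rate of catheterization". The rule has two branches written with paired parentheses. An upper limit below the margin leads to the first verdict and an upper limit at or above it leads to the second: "then we will conclude that the FAST voiding trial is non-inferior (inferior) to the Traditional voiding trial". There is no third branch. The same paragraph uses δ for the FAST-minus-Traditional difference and then says that this difference "is the margin of non-inferiority and will be set at 10" percent.

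The Sample Size Considerations section is worded differently. It says that "the FAST voiding trial will be considered non-inferior to the Traditional voiding trial if the difference in the rate of catheterization" between the groups is less than δ = 10%. It writes the true difference as d, and sets H0: d ≥ δ against HA: d < δ. It describes only when FAST counts as non-inferior and never defines a finding of inferiority.

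Statistical Methods adds that "The test for non-inferiority will also be performed according to surgery type", so the two-branch rule also governs those tests.

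**The concern.** Under the plan's own hypotheses, an upper limit of 10 points or more means that H0 was not rejected. The rule turns this into acceptance of H0, a positive finding that FAST is inferior. To show that FAST is worse, the lower limit would have to exclude zero. To show that it is worse by the margin, the lower limit would have to reach 10 points. The plan refers to neither.

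At stake is what the trial may report. A truly equivalent FAST method could be published as inferior on data that are merely imprecise. The surgery-type tests use fewer patients and so have wider intervals, which makes the false label more likely there.

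**Working it through.** **Inputs** (section 12): Traditional rate 5%, FAST rate 5%, margin 10 points, 59 per arm passing the voiding trial, 80% power, two-sided 95% interval. The plan names no interval method, so Wald and Newcombe limits are shown as a range.

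**1. The plan's own figure.** The plan states that "a sample size of 59 per group (n=118 total) will yield 80% power". With unpooled variance and the normal approximation:

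n = (z₁₋α + z₀.₈₀)² × [pF(1−pF) + pT(1−pT)] / δ²

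- One-sided α = 0.05: (1.645 + 0.842)² × 2 × 0.05 × 0.95 / 0.01 = 58.7, so 59. The same formula, with the denominator (δ − d)² for unequal rates, reproduces the whole sample-size table (109, 80, 59, 44, 33).
- One-sided α = 0.025, which matches the planned two-sided 95% interval: 75 per arm.

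The standard error at 59 per arm is √(2 × 0.05 × 0.95 / 59) = 0.0401. Power is Φ(0.10/0.0401 − 1.645) = 0.80, or Φ(0.10/0.0401 − 1.960) = 0.70 with the 95% interval.

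**2. How often the label appears when the methods are equal.** Under the two-branch rule, P(labelled inferior) = 1 − power. At the stated power this is 1 − 0.80 = 20%, whatever the interval method. Exact enumeration of all 60 × 60 possible tables, at true rates 5% and 5% and 59 per arm, gives:

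| Interval | Labelled inferior | Labelled, and interval includes zero | Share of labels |
|---|---|---|---|
| 90% Wald (matches the 59) | 20.7% | 15.8% | 76% |
| 95% Wald | 28.6% | 25.6% | 90% |
| 95% Newcombe | 41.4% | 40.1% | 97% |

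**3. When FAST is truly better** (4% against 5%, a row of the plan's table): the label appears in 11.9% (90% Wald), 17.4% (95% Wald) or 28.8% (95% Newcombe) of trials.

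**4. Examples at 59 per arm, 95% Wald.**
- 4/59 against 3/59: 0.0169 ± 1.96 × 0.0435 = −6.8 to +10.2 points, Fisher p = 1.0. The rule says inferior.
- 5/59 against 5/59: 0 ± 1.96 × 0.0513 = −10.05 to +10.05 points. The rule says inferior although the observed rates are identical.

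The second pattern is rare. A label with an observed FAST rate no higher than Traditional occurs in 1.2% (95% Wald) to 4.2% (95% Newcombe) of trials with equal true rates.

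**5. Surgery-type tests.** Stratum sizes are not given. If about 30 per arm passed the voiding trial in a stratum (assumption), equal 5% rates would give the label in 43% (95% Wald) to 76% (95% Newcombe) of trials.

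**6. Rules based on the lower 95% limit** (59 per arm).
- Lower limit above 0, equal 5% rates: label in 3.0% (Wald) or 1.3% (Newcombe) of trials.
- Lower limit at or above 10 points, equal 5% rates: below 0.01%. With true rates of 15% and 5% it is met in only 2.3% of trials (Wald).

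**The case against.** The strongest reply is that this is one parenthetical word. The formal hypotheses are right, the aim is stated throughout as showing that FAST is not inferior, and the interval must be computed, so a careful reader would see that −6.8 to +10.2 points is inconclusive. The estimate, the success criterion and the sample size are unaffected. The 1-in-5 figure is also the type II error that the plan already accepts. Those trials would miss non-inferiority under any wording, and the correction changes only what the miss is called.

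All of that is accurate and limits the weight of the point. It does not remove it. Statistical Methods holds the operative decision rule and says what will be concluded. A pre-specified rule should not depend on its authors departing from it. A type II error reported as *not demonstrated* is an acceptable risk; the same error reported as *inferior* is a false finding.

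Two further cautions stand. The share of labels whose interval includes zero is 76% for the 90% interval that underlies the 20.7%, and reaches 90% to 97% only with the planned 95% interval. The double use of δ is editorial, since the 10% figure and the notation in the sample-size section leave one workable reading.

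**Conclusion.** The concern holds. The rule is wrong as written, because it treats failure to reject H0 as proof of inferiority, and nothing else in the document corrects it. It should be fixed.

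With equal true rates of 5%, the false label appears in 20% of trials at the stated power. With the planned 95% interval at 59 per arm the figure is 28.6% to 41.4%, depending on the interval method. The excess over 20% belongs to the separate mismatch between the sample size and the 95% interval, and to the unnamed interval method, not to this wording. The logical fault depends on none of these figures. The error runs only against FAST and cannot create a false non-inferiority claim. When the label is applied, FAST is usually numerically worse, but that is not evidence of inferiority.

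**What to change.** In Statistical Methods, adopt the notation of the sample-size section: d for the FAST-minus-Traditional difference and δ = 10% for the margin. Then state that FAST is non-inferior if the upper limit of the two-sided 95% interval for d is below δ, and that otherwise non-inferiority has not been demonstrated. Use the same wording for the surgery-type tests, which can stay as pre-specified.

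The simplest course is to drop the verdict of inferiority. If it is kept, tie it to a lower-limit criterion stated in advance and say what it means. A lower limit above 0 means worse than Traditional, not worse by the margin; with Wald limits it would label 4/59 against 0/59 (+0.4 to +13.2 points, Fisher p = 0.12). A lower limit at or above 10 points means worse by the margin, but would rarely be met at this size.

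The cost is one or two sentences, with no extra patients, data or tests. More results will be reported as inconclusive: with equal 5% rates, 59 per arm and a lower-limit-above-0 criterion, 25.6% (Wald) to 40.1% (Newcombe) of trials.

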# 12. STATISTICAL ANALYSIS

- *Describe how your data will be used to test the hypotheses.*
- State clearly what variables will be tested and what statistical tests will be used.
- *Include sample size calculations.*
- If this is a pilot study, state which variables will be examined for hypothesis generation in later studies.

This is a randomized controlled trial in women to compare two methods of voiding after undergoing surgical repair for pelvic organ prolapse [POP]. The two methods are: the traditional retrograde bladder filling method and the force of stream trial (FAST). The study is designed as a non-inferiority trial to demonstrate that among patients who are discharged without a urinary catheter (because they passed the post-op voiding trial), the rate of catheterization within the six-week post-operative period in subjects undergoing the FAST voiding trial is not worse than in subjects undergoing the traditional retrograde voiding trial.

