# **Intention-to-Treat (ITT)**

Version Date: 2/26/16 Page 10 of 25

All subjects will be analyzed according to the intention-to-treat [ITT] principle. A patient will be considered evaluable and will be included in the intention-to-treat analysis if the patient was randomized to either voiding trial group and able to undergo the voiding trial after surgery. Analyses that take into account the actual voiding trial received will be carried out as a secondary analysis (per protocol [PP] analysis).

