  - d. The Kaplan-Meier product limit method will be used to estimate time-to-catheterization post-discharge and the two groups (Traditional Retrograde vs. FAST) will be compared using the log-rank test. Median time-to-catheterization will be estimated along with their corresponding 95% confidence intervals. The feasibility of this analysis will depend on the observed catheterization rates.
  - e. A mixed models approach to repeated measures analysis of variance (MM-RMANOVA) will be carried out, separately, for each of the two measures of patient satisfaction with post-operative bladder function (AUASS and UDI-6). Each model will examine if the patterns of change in satisfaction scores across

Version Date: 2/26/16 Page 11 of 25

time (baseline, 2 weeks post-op and 6 weeks post-op) differ between the two voiding methods. The models will include voiding group (Traditional/FAST), time (baseline, 2 weeks post-op and 6 weeks post-op) and a group-by-time interaction term. Data transformations may be employed if standard model assumptions are not met. If no suitable transformations are found, then appropriate non-parametric methods may be used instead.

A secondary analysis using logistic regression, will be carried out for each of the aims 2a, 2b and 2c, including explanatory variables such as age, site, and surgery type (sling vs. no sling).

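### The non-inferiority test is confined to women who pass their assigned voiding test, and no combined as-randomised estimate of catheter use is planned beside it

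*Combined protocol and SAP*

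**What the plan says.** The primary outcome in Sections 10 and 12 is catheterisation up to six weeks in women who left hospital without a catheter. The opening of Section 12 places the comparison "among patients who are discharged without a urinary catheter (because they passed the post-op voiding trial". The Statistical Methods text sets a 10-point margin and the decision sentence "then we will conclude that the FAST voiding trial is non-inferior (inferior) to the Traditional voiding trial". Its next paragraph limits the test to "catheterization within the six-week post-operative period among subjects who were discharged without needing a urinary catheter". The Sample Size Considerations repeat the limit and name these women as the population of main interest.

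The Intention-to-Treat paragraph says "All subjects will be analyzed according to the intention-to-treat [ITT] principle". It counts a woman as evaluable "if the patient was randomized to either voiding trial group and able to undergo the voiding trial after surgery", so its set includes women who fail.

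Failure at discharge is a separate secondary outcome. A chi-square or Fisher test compares "the proportion of subjects who are sent home with a catheter due to failure of their voiding trial", and "A secondary analysis using logistic regression, will be carried out for each of the aims 2a, 2b and 2c" covers it with adjustment.

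Section 11 gives the pass rules. Traditional uses the volume voided out of 300 cc. FAST uses the patient's VAS rating of her stream and, when that is below 50, a bladder-scan residual. Section 11 also describes randomisation following consent, with the voiding test on the morning after surgery.

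**The concern.** Randomisation makes the arms comparable as randomised. It does not guarantee that passers of one test are comparable with passers of another. Some routes to failure are alike (no void under Traditional, no urge within 20 minutes under FAST), but otherwise different rules decide who enters each primary denominator.

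The primary therefore answers a legitimate but conditional question: how often does a pass prove wrong? It does not say which test leaves fewer women with a catheter overall. That second question matters to the plan's own rationale, since Section 3 cites the burden of catheterisation and Section 19 hopes that results will help reduce it.

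If failure rates differ between arms, the two answers can separate. The plan supplies the pieces but no combined figure specified in advance. Separately, surgical exclusions that arise after allocation remove women from the evaluable set, and no account of them by arm is specified.

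**Working it through.** **1. The plan's own chain.** Inputs from Sample Size Considerations: 5% later catheterisation in passers of both tests, margin 10 points, 80% power, 30% failing each test.

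- The unpooled formula at one-sided 0.05 gives (1.645 + 0.842)² × 2 × 0.05 × 0.95 / 0.10², just under 59. This is the stated 59 passers per group.
- 118 × 1.3 = 153.4, rounded up to 154, or 77 evaluable per arm.

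The choice of alpha and the method of inflation are separate matters. Only the 5%, the 30% and the 77 are used below.

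**2. Any catheter use over all evaluable women.** With failure rate f and later risk p in passers, any use = f + (1 − f) × p.

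- Plan's inputs, each arm: 0.30 + 0.70 × 0.05 = 33.5%. Passers 5% vs 5%. No divergence.
- Rates of the sling trial described in Section 3: Traditional 0.255 + 0.745 × 0.05 = 29.2%; FAST 0.26 + 0.74 × 0.05 = 29.7%. About half a point.

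**3. If failure rates differ (assumed).** The plan assumes that "approximately 30% in the FAST voiding trial arm will fail the test", the same as for Traditional. The comparison described in Section 3 was in midurethral sling surgery, and Sections 2 and 3 say that no randomised trial exists in apical prolapse surgery, so equality is an assumption. Keep Traditional at 30% and p at 5% in all passers. The difference in any use is then 0.95 × (f_FAST − f_Trad).

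| FAST failure | Passers' difference | Any use, FAST | Any use, Traditional | Difference (points) |
|---|---|---|---|---|
| 20% | 0 | 24.0% | 33.5% | −9.5 |
| 25% | 0 | 28.75% | 33.5% | −4.75 |
| 30% (plan) | 0 | 33.5% | 33.5% | 0 |
| 35% | 0 | 38.25% | 33.5% | +4.75 |
| 40% | 0 | 43.0% | 33.5% | +9.5 |

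**4. Opposite signs need more assumptions.** Suppose that FAST fails 20%, its passers include every woman who would pass Traditional, and the extra 10% of women have later risk r. Later catheterisation over all FAST women is 0.035 + 0.10 × r.

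- r = 10%: later 4.5%; passers 4.5/80 = 5.6% vs 5.0%; any use 24.5% vs 33.5%.
- r = 20%: later 5.5%; passers 5.5/80 = 6.9% vs 5.0%; any use 25.5% vs 33.5%.

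**5. Precision at 77 per arm (95% half-widths).**

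- Any use, 33.5% in both arms: 1.96 × √(2 × 0.335 × 0.665 / 77) = 14.9 points.
- Discharged with a catheter, 30% in both arms: 14.5 points.
- Later catheterisation over all evaluable women, 3.5% in both arms: 5.8 points.

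**6. Order of allocation and surgery.** Section 11 puts randomisation after consent and describes the voiding test as following surgery. Section 7 excludes women with a cystotomy at surgery. Sample Size Considerations list, as the first of three groups of randomised subjects, those with a surgical complication needing prolonged catheterisation. Read together, allocation precedes surgery and some exclusions follow allocation.

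**The case against.** The strongest reply is that the plan is candid. A reader might infer from the decision sentence alone that the Statistical Methods text drops the restriction. It does not: the next paragraph carries it, as do the outcome, aims and sample-size text. The sample-size section also leads from evaluable women to passers, and the Intention-to-Treat paragraph contrasts its analysis with one by test actually received, so it may mean only analysis by assigned arm. All of this stands. The wording edits are clarifications.

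A reader might also infer that catheter use over all evaluable women is never examined. That is not so either, because catheterisation at discharge is a planned secondary outcome with adjusted regression. It makes up 30 of the 33.5 points of the combined measure, and with equal risk in passers the combined difference is only 0.95 times the failure difference. So the combined figure adds most when later risk differs as well. A reader could also derive it from reported counts.

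What remains is that the Statistical Methods text plans tests, with no stated interval, for the discharge component, and no combined estimate is fixed in advance. On timing, the exact moment of randomisation is not given, but the group of randomised women with surgical complications supports the reading above. Silence on reporting by arm does not prove that it would be omitted.

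**Conclusion.** The point holds as a modest design improvement. The non-inferiority comparison is made in a subset fixed after randomisation by the assigned test's own rule. It is therefore conditional on passing and not a full intention-to-treat comparison, and no combined as-randomised estimate of catheter use is planned to accompany it.

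On the plan's inputs the divergence is zero, and with the cited sling-trial rates it is about half a point. Larger gaps, such as ±9.5 points for FAST failure of 20% or 40%, rest on assumed failure rates and a common 5% later risk. Opposite signs also need nested passers and a 10–20% risk in the extra passers.

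A reader might go further and infer that the passers' result is biased, or that it favours FAST. The documents do not support either: they do not establish what the failure rates will be in this population, and the arithmetic shows only that the two measures answer different questions.

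**What to change.** Keep the primary outcome, margin and sample size.

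1. In the Intention-to-Treat paragraph, state: *Evaluable women are analysed in the arm to which they were randomised. The primary analysis is conditional on passing the assigned test and is not a full intention-to-treat comparison.* Repeating the restriction in the decision sentence would help but is optional.
2. In Statistical Methods, add a supportive estimate, not a second gate: *the FAST minus Traditional difference, with 95% CI, in any catheter use (at discharge or later, to six weeks) over all evaluable women as randomised, shown beside its two components.* The data are already collected. The downsides are imprecision (about ±15 points) and equal weight for a discharge catheter and a later catheterisation, so the components must be shown.
3. Allocate after surgery and before the day-1 voiding test, so that surgical exclusions come first. The Randomization section leaves its procedural details open. The cost is that someone must use the web system after surgery, and the documents do not address staffing for this. If it is not possible, report randomised but non-evaluable women by arm, with reasons.

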#### **Primary Outcome:**

The primary outcome variable of interest is the rate of catheterization within the six-week post-operative period following surgical repair of POP, among those discharged without a urinary catheter. (The primary outcome will be the overall rate (regardless of stratification) but catheterization rates by surgery type will also be examined.)

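### The non-inferiority test, with its two-way verdict, is repeated within each surgery type, where it has only about 24–40% power (equal strata assumed), so a false finding of inferiority in at least one type is likely

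*Combined protocol and SAP*

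**What the plan says.** All references are to Section 12 of the combined protocol and SAP.

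- **Test.** Under Statistical Methods, the primary comparison is "carried out using a two-tailed 95% confidence interval" for the FAST minus Traditional difference. That difference "is the margin of non-inferiority and will be set at 10" percent.
- **Verdict.** If the upper limit is below the margin (at or above it), "then we will conclude that the FAST voiding trial is non-inferior (inferior) to the Traditional voiding trial". There is no third, inconclusive outcome.
- **Strata.** The same section continues: "The test for non-inferiority will also be performed according to surgery type (the stratification variable". No separate margin, confidence level, power or caveat is given for the strata.
- **Status.** Under Primary Outcome, the overall rate is primary, and "catheterization rates by surgery type will also be examined".
- **Sample size.** Under Sample Size Considerations, "a sample size of 59 per group (n=118 total) will yield 80% power". This concerns the overall comparison only. No figure is given for either surgery type, and the expected sling/no-sling split is not stated.

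**The concern.** The overall test was sized for 59 women per arm who pass the voiding trial. Each surgery-type test has about half of them, or fewer in the smaller stratum, but faces the same margin and the same 95% interval. A stratum can easily miss the margin through imprecision alone, and the rule turns that miss into a statement that FAST is inferior in that type of surgery.

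The randomized FAST evidence described in Section 3 comes from midurethral sling surgery, so readers will look closely at the result in women without a sling. If the two methods are equivalent, the plan as written would usually publish a prespecified but false finding against FAST in at least one surgery type.

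**Working it through.** **Inputs.** Margin 10 points; two-tailed 95% interval; 1:1 allocation; 154 evaluable women; 30% failing the voiding trial. The control rate is as stated ("the rate of catheterization during the six-week post-operative period is about 5" percent), and FAST is assumed equal to it. Assumed here because the documents are silent: the interval method and the share of women in each surgery type.

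**The plan's own figure.** With both rates at 5%, n per arm = (z_α + z_β)² × 2 × 0.05 × 0.95 / 0.10².

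- One-sided 0.05: (1.645 + 0.842)² × 0.095 / 0.01 = 58.7, so 59. This reproduces the plan.
- One-sided 0.025, which is what a two-tailed 95% interval implies: (1.960 + 0.842)² × 0.095 / 0.01 = 74.6, so 75.

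The 59 therefore does not match the stated interval, nor the sample size table, described as "using a 2-sided alpha level of 0.05". That is a separate point. It matters here because overall power under the planned interval is already about 70% at 59 per arm and 66% at 54 (normal approximation).

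**Stratum size.** 154 × 0.70 = 107.8 passers, or about 54 per arm. With two equal strata, 154 × 0.70 / 4 = 26.95, or about 27 per arm per stratum. If all 118 planned passers were obtained it would be 118 / 4 = 29.5.

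**Precision at 27 per arm.** At the assumed rates the normal half-width is 1.96 × √(2 × 0.05 × 0.95 / 27) = 11.6 points, wider than the 10-point margin.

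**Upper limits for particular results at 27 per arm (FAST vs Traditional).**

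| Events | Wald | Newcombe |
|---|---|---|
| 0 vs 0 | 0% (passes) | 12.5% (fails) |
| 0 vs 1 | 3.4% (passes) | 9.1% (passes) |
| 1 vs 1 | 10.07% (fails) | 14.9% (fails) |

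Two of these by hand. Wald 1 vs 1: 1.96 × √(2 × (1/27)(26/27) / 27) = 0.1007. Newcombe 0 vs 0: z² / (n + z²) = 3.84 / 30.84 = 0.125.

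**Chance that a stratum passes.** For each pair of event counts (x, y), take the product of the two binomial probabilities at 5%, and sum over the pairs whose upper limit is below 10%. At 27 per arm this gives 40% (Wald), 31% (Agresti–Caffo), 27% (continuity-corrected Wald) and 24% (Newcombe or score). The normal approximation gives 39%.

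**Chance that at least one stratum fails.** The strata contain different women, so this is 1 − (p₁ × p₂), where p₁ and p₂ are the chances of passing.

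| Passers per arm in the two strata | Wald: each passes | Wald: at least one fails | Newcombe: each passes | Newcombe: at least one fails |
|---|---|---|---|---|
| 27 / 27 | 40%, 40% | 83.9% | 24%, 24% | 94.1% |
| 30 / 29 (all 118 pass) | 57%, 51% | 71.1% | 24%, 24% | 94.3% |
| 32 / 22 | 54%, 36% | 80.5% | 25%, 11% | 97.4% |
| 38 / 16 | 52%, 44% | 77.1% | 35%, 9% | 97.0% |
| 43 / 11 (80/20 split) | 57%, 57% | 67.5% | 45%, 1% | 99.6% |

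The Wald figures do not fall steadily with n because a 0 vs 0 result has a Wald limit of exactly zero and passes at any size.

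**What adequate strata would need.** 75 passers per arm per stratum gives 75 × 4 = 300 passers, and 300 / 0.70 ≈ 429 evaluable women, against 154 planned.

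**The case against.** Several counter-arguments carry weight.

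- **The strata are secondary.** Primary Outcome makes the overall rate primary, so the stratum tests change neither the primary conclusion nor its error rate. This stands, and it limits the seriousness of the point.
- **The harm depends on the label.** A failed stratum is a wrong verdict only because the rule calls it inferior. Were it read as non-inferiority not shown, the statement would be accurate. This stands too, but the stratum tests would still have low power, and no rule would link a stratum's claim to the overall result.
- **A reader might infer that a stratum of this size cannot pass, or that one will almost surely fail.** The documents support neither. At 27 per arm a stratum passes in 24–40% of trials; 0 vs 1 event passes even with Newcombe. With Wald, 1 vs 1 passes from 28 per arm (9.72%). Probabilities of 94% and above arise only if a Newcombe or score interval is chosen, and the plan names none.
- **A reader might infer that three tests inflate the trial's false-positive rate.** In simulation at 5% vs 15%, any of the three passes in 9.6–12.0% of trials with Wald, against 3.4–4.3% for the overall test alone; with Newcombe, 4.4–4.9% against 2.1–2.2%. But the plan does not present the three as equal claims, so this is not an error rate for its primary conclusion.

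**Conclusion.** The point holds as a should-fix. The plan orders a formal test with a two-way verdict in strata for which it was not sized. With equal strata of about 27 per arm and true rates of 5% in both arms, each stratum test has about 24% (Newcombe) to 40% (Wald) power. At least one surgery type would wrongly be labelled inferior in about 71–84% (Wald) or 94–97% (Newcombe) of trials for smaller-stratum shares of 30–50%; an 80/20 split extends this to 68% and 99.6%.

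These figures rest on the plan's own 5% rates, on 54 to 59 passers per arm, and on an assumed split and interval method.

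**What to change.** Under Statistical Methods, delete the sentence that runs the non-inferiority test by surgery type and replace it with:

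> For each surgery type the risk difference and its 95% confidence interval will be reported descriptively; no non-inferiority or inferiority verdict will be given by surgery type, and the only confirmatory test is the overall one.

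This agrees with Primary Outcome, which only has the rates by surgery type examined. The interval method should be named at the same time.

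An estimate of the method-by-surgery-type interaction is optional. It would be very imprecise: 5% of 108 to 118 passers is about 5 to 6 events, spread over four cells.

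The cost is one change of wording, with no effect on sample size or conduct. The investigators give up subgroup verdicts that the trial was not sized to support.
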